2.4 Sample size calculation

Much of the following is copied or adapted from the THPP+ protocol paper.¹

The primary power calculations for the THPP+ study are for the c-RCT comparisons of perinatally depressed women and their children in the control vs. intervention arms at 36 months postnatally at the 5% two-tailed significance level. As with the THPP trial,² we assume 40 village clusters randomized in a 1:1 allocation ratio within 11 union councils with 14 perinatally depressed women per village cluster to yield a total sample size of 560 perinatally depressed women at baseline. In addition, for THPP+, we recruit 14 perinatally non-depressed women per village cluster for a total of 560 perinatally non-depressed women at baseline. We conservatively estimate that loss to follow-up (including infant mortality and maternal illness and death) of both perinatally depressed and perinatally non-depressed women at 36 months will be 20%. Therefore, the total sample size available at 36 months is anticipated to be 480 perinatally depressed and 480 perinatally non-depressed women and their children. Using standard formulae^{3,4} for a cluster randomized design and assuming intra-cluster correlation of 0.07 in the intervention arm and 0.05 in the control arm, the trial will have 90% power at 36 months to detect a difference in perinatally depression remission of 65% in perinatally depressed-Intervention vs. 45% in perinatally depressed-control for the anticipated total sample size of 480 perinatally depressed women at 36 months. For child outcomes, this sample size will yield power of more than 90% to detect a difference between arms in mean total difficulties (TD) score (range 0-40) of 3 points for children of perinatally depressed mothers using plausible estimates for intra-cluster correlations of 0.04-0.08⁵ and 5.2 for standard deviation for the TD score among 3 year olds.⁶

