Secondary comparisons mainly focus on child outcomes and are well powered. For the secondary hypothesis of equivalence between children of perinatally depressed mothers in the intervention arm and perinatally non-depressed mothers in the control arm, we will conclude equivalence if the 95% CI for the difference between the mean score in the two groups lies between -2 and 2 units. We note that differences of 1.0-2.0 points are often observed between boys and girls^{6,7}. With 220 children in each group and conservatively assuming an overall significance level of 2.5% (corresponding to the 95% CI), an SD of 5.2 and ICC of 0.04, and no difference between the groups, we will have 83% power to conclude equivalence.^{3,8} For the secondary research question of the community benefit (i.e. carryover) of the intervention for perinatally non-depressed women and their children, we will have 80% power to detect a 1.7 or greater impact of the intervention on mean TD score (Groups perinatally non-depressed-Intervention vs. perinatally non-depressed-Control, Figure 1) for the same assumptions of the primary comparison above.

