2.7 Time of outcome assessment and visit windows

For all analyses, time will be measured from the date of delivery. Outcome data (depending on the outcome) are collected at 3, 6, 12, 24, and 36 months postnatal. The protocol defined the visit window to be from four weeks (28 days) before to four weeks (28 days) after the scheduled visit date for all mother outcomes. No in-window vs. out-of-window adjustments will be taken into account.

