GEE analyses with a **log-link** and **Poisson distribution** will be used for **binary outcomes** in order to estimate prevalence ratios. The GEE analyses will apply the Kauermann-Carroll small-sample corrections with a t-test for inference.^{14,15} The GEE analyses will take into account clustering using an exchangeable working correlation matrix, and robust standard errors to account for potential model misspecification. All mixed models will include village cluster as a random intercept to account for the clustered study design. (Note that a separate random intercept for each group [intervention, control, non-depressed] was considered and formulated in section 3.1.1.1, but model convergence issues led us to revert to a single random intercept for cluster.) Additionally, clustering by peer group within the intervention arm will be potentially taken into account by adding an additional random intercept for each peer group.

Primary analyses of outcomes measured at a single follow-up time point are designed to include the following fixed factor variables: group (non-depressed, depressed intervention, depressed control), strata (11 Union councils), and any variables found to be imbalanced by loss to follow-up or at baseline (determined using $p < 0.10$). Under the assumption that those covariates explain the missing data mechanism, we will obtain valid estimates of the intervention effects using the complete case data (i.e. without the need for imputation or an alternative method).¹⁶ If there are concerns or evidence that covariates cannot explain the nature of the missingness (i.e. if the data are missing not at random), we will perform a series of sensitivity analyses based on the pattern mixture approach.¹⁷

Model assumptions will be assessed using examination of the residuals from the model and tests for linearity. In the presence of a ceiling or floor effect, we will also model the outcome using mixed effects tobit regression, which may allow us to more appropriately model the mean in such a situation.

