3.1.1 Analysis models and code

For a continuous variable measured and/or analyzed at a single time point, we have the following model formulation (assuming no clustering at the peer group level and assuming one random intercept for cluster), which can easily be extended to the tobit framework:

$$Y_{jk} = \alpha_1 + \beta_1 X_{1jk} + \beta_2 X_{2jk} + \beta_3 U_k + \beta_5 C_{jk} + b_{0k} + \epsilon_{jk},$$

$$b_{0k} \sim N(0, \sigma_{b_{0k}}^2), \epsilon_{jk} \sim N(0, \sigma_{\epsilon_{jk}}^2)$$

for the j^{th} mother-child dyad in the k^{th} village cluster.

The fixed effects terms are as follows:

- Y_{jk} is the continuous outcome of interest
- X_{1jk} is a dummy variable for perinatally depressed intervention vs. control (1 if intervention; 0 if control) for mother j in cluster k
- X_{2jk} is a dummy variable for perinatal non-depressed vs. perinatally depressed control (1 if non-depressed; 0 if control) for mother j in cluster k
- U_k is the union council within which cluster k is located
- C_{jk} are other adjustors

The two random effects terms are as follows:

- b_{0k} is a random intercept for cluster k
- ϵ_{jk} is the residual measurement error for mother/child j in cluster k

This model can be fit with the following Stata code (with no additional adjustors):

```
mixed sdqTotal i.arm3 i.ucCode || clusterCode:, reml dfmethod(repeated)
```

Estimates of the pre-specified comparisons of interest will be derived from the fitted model.

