3.3 Moderator analyses

Secondary analyses focus on potential moderators (effect modifiers) of any main associations with the primary outcomes. *A priori*, we hypothesize the following baseline variables may impact the degree to which the intervention affects depression symptoms, with their specific categorizations given in Table 2: socioeconomic status (education, asset index), maternal education (none vs. any) household composition (nuclear family status), child gender, the presence of intimate partner violence, treatment expectations (very/moderately useful vs. somewhat/not useful), maternal age (18-24 vs. 25+), depression severity (PHQ-9 = 10-14 vs. 15+), and depression chronicity (<12 weeks vs. ≥12 weeks). For the maternal outcomes, we will also look at parity (4+ kids vs. <4 kids) as a moderator. We will test for moderation of the effect by including these potential moderators in the model as an interaction between the potential moderator and the intervention indicator. Specifically, for our primary outcomes, we now have:

$$Y_{jk} = \alpha_1 + \beta_1 X_{jk} + \beta_2 M_{jk} + \beta_3 X_{jk} M_{jk} + \beta_4 U_k + \beta_5 C_{jk} + b_{0k} + \epsilon_{jk},$$

$$b_{0k} \sim N(0, \sigma_{b_{0k}}^2), \epsilon_{jk} \sim N(0, \sigma_{\epsilon_{jk}}^2)$$

where X_{jk} is the indicator of perinatally depressed intervention vs. control (1 if intervention; 0 if control) for mother i in cluster j and M_{jk} is the moderator variable for mother-child dyad j in cluster k . Other parameters are defined as in Section 3.1.1. β_3 tests the strength of the effect modification, and intervention effects by levels of the moderators can be estimated from this model.

4 References

3. Julious SA. Tutorial in biostatistics - Sample sizes for clinical trials with normal data. *Stat Med*. 2004;23(12):1921-1986.

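### Child sex enters the SDQ-TD models only if it shows imbalance at p<0.10; naming it as a fixed covariate would be a free, minor improvement

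*SAP*

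**What the plan says.** SAP 2.4, next to the ±2 equivalence margin, remarks: "We note that differences of 1.0-2.0 points are often observed between boys and girls". SAP 3.3 lists child sex among the baseline variables that may modify the effect ("household composition (nuclear family status), child gender, the presence of intimate partner violence"), and Table 2 repeats it. It is therefore available for analysis.

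SAP 3.1 gives the fixed effects of the primary single-time-point models as group, the 11 union councils, and "any variables found to be imbalanced by loss to follow-up or at baseline (determined using $p < 0.10". It does not list which variables are screened.

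SAP 3.1.1 writes the model with a covariate term, described only as "are other adjustors". It then gives code, introduced by "This model can be fit with the following Stata code (with no additional adjustors", and the line is "mixed sdqTotal i.arm3 i.ucCode || clusterCode:, reml dfmethod(repeated". No section of either document names child sex as a fixed main effect in the primary child model.

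**The concern.** Protocol 3.3 relies on the SDQ at 36 months, and the assessment timetable shows it only in the last column. There is no earlier SDQ score to adjust for, so any gain in precision must come from other predictors. Child sex is the one predictor of SDQ-TD whose size the SAP states, and an intervention that begins in the third trimester cannot change it.

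The p<0.10 rule handles such a variable awkwardly. It admits a covariate because it is imbalanced, whether or not it predicts the outcome. It leaves out a real predictor that happens to be balanced. It also leaves the final form of the primary model to the data. At stake is a little precision in the SDQ-TD effect, in the ±2 equivalence interval and in the carryover test, plus whatever sex imbalance falls just short of the threshold.

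**Working it through.** **Inputs from SAP 2.4.** SD 5.2; ICC 0.04 for equivalence and 0.04-0.08 for the primary comparison; 220 children per group for equivalence; 40 clusters allocated 1:1, so 20 per arm and 220/20 = 11 children per cluster; margin ±2; carryover difference 1.7; primary difference 3, tested "at the 5% two-tailed significance level"; boy-girl difference d = 1 to 2 points.

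**Assumptions.** Half the children are boys, and d applies in this population.

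**1. The plan's own figures.**
- SE = 5.2 × √(2 × [1 + 10 × 0.04] / 220) = 0.587.
- Equivalence power = 2Φ(2/SE − c) − 1. With c = 2.024 (t, 38 df) this is 2Φ(1.385) − 1 = 83.4%, against 83% stated. Plain z (1.96) gives 85.3%.
- Carryover power = Φ(1.7/SE − 2.024) = Φ(0.874) = 80.9%, against 80% stated. The SAP refers here to the primary comparison's assumptions without fixing one ICC; 220 per group and ICC 0.04 reproduce its figure.

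**2. Share of variance due to sex.** A 50:50 binary covariate with difference d contributes d²/4, which is 0.25 (d = 1) or 1.00 (d = 2). Total variance is 5.2² = 27.04, so the share is 0.9% to 3.7%.

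**3. Adjusted SE.** Within-cluster variance is 0.96 × 27.04 = 25.96 and between-cluster variance is 0.04 × 27.04 = 1.08. Adjusted SE = √(2 × [(25.96 − d²/4)/220 + 1.08/20]).

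| | Unadjusted | d = 1 | d = 2 |
|---|---|---|---|
| SE | 0.587 | 0.585 | 0.579 |
| SE reduction | – | 0.3% | 1.3% |
| Equivalence power | 83.4% | 83.7% | 84.8% |
| Carryover power (1.7 points) | 80.9% | 81.1% | 81.9% |

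**4. Primary 3-point contrast.** Take 240 per arm (the SAP's 480 divided by 2), 12 per cluster and c = 1.96. At ICC 0.04 the SE is 0.570 and power goes from 99.95% to 99.96%. At ICC 0.08 the SE is 0.651 and power goes from 99.6% to 99.6-99.7%. (A 20% loss from 560 would leave 448, or 224 per arm, rather than 240; power still exceeds 99%.)

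**5. Imbalance that the p<0.10 rule lets through.** With 220 per group, the SD of the difference in the proportion of boys is √(2 × 0.25/220) = 0.048.
- A 1-SD imbalance moves the contrast by 0.05 to 0.10 points.
- The largest imbalance that escapes is about 1.645 × 0.048 = 0.078, or 7.8 percentage points. This treats the screen as a two-group test that ignores clustering. It moves the contrast by 0.08 to 0.16 points, or 13-27% of the SE.
- Equivalence passes only if the observed difference is at most 2 − 2.024 × 0.587 = 0.81, so that extreme case uses about 10-19% of the room.

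**The case against.** - **The code line is a template.** It is labelled as the version without adjustors, and the equation above it has a covariate term that SAP 3.1 fills. A reader might infer from the code alone that the primary model excludes child sex. The documents do not support that: sex enters when it meets the p<0.10 rule, provided it is among the variables screened, which SAP 3.3 suggests but SAP 3.1 does not state.
- **Sex is examined elsewhere.** The moderator model in SAP 3.3 includes the moderator's main effect. This stands, but that analysis is secondary and covers depressed mothers' dyads only.
- **Chance imbalance is not bias.** A reader might infer that omitting sex leaves imbalance in every child contrast. For the randomised contrasts, chance imbalance is already in the unadjusted SE and averages to zero, so step 5 is largely another view of the precision loss in step 3, taken at the edge of the threshold. The equivalence contrast also differs by screening status, so randomisation alone does not protect it, but the documents give no sign that child sex varies with screening status.
- **The 1-2 point figure is soft.** It is offered as context for the margin and cites normative data and a study of 5-6 year olds. It concerns the SDQ only, so it supports no claim about the Bayley scores.
- **Child age.** SAP 2.7 defines a window for mother outcomes only and adds "No in-window vs. out-of-window adjustments will be taken into account". A reader might infer that age at assessment should be adjusted for as well. The documents give no age slope for SDQ-TD, and age at assessment is set after randomisation, so that is not established.
- **The calculation is simpler than the model.** It uses two groups of 220, whereas the coded model pools non-depressed women across arms and cannot itself yield the carryover contrast. The sizes are therefore approximate.
- **Timing.** SAP version 5.0 is dated October 14, 2019, after the stated end of the trial in August 2019. Its note on convergence problems suggests that some models may already have been run, so a late change to the primary model has a cost in credibility. This stands and shapes the fix.

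**Conclusion.** The point holds as a minor, essentially free improvement. The SAP makes adjustment for child sex in the SDQ-TD models depend on an imbalance test, although it states a 1-2 point sex difference itself and has the variable. Naming the covariate in advance is better than screening for it, because it captures the precision whether or not sex is balanced and removes one data-driven choice.

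The gain is small: 0.3 to 1.4 percentage points of equivalence power, 0.3 to 1.1 of carryover power, and under 0.1 for the primary 3-point contrast. These sizes rest on the SAP's SD and ICC, an even sex ratio, and the 1-2 point range holding for three-year-olds in this setting, which the documents do not show. Nothing here suggests that the planned primary child result would be biased or underpowered.

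**What to change.** In SAP 3.1, name child sex as a fixed covariate for SDQ-TD, included regardless of observed imbalance. Add the matching factor term to the fixed part of the Stata line in 3.1.1, and include it in whatever model produces the equivalence and carryover contrasts.

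Date the change, state whether 36-month outcome data had been seen, and report the version 5.0 model alongside it.

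The cost is one SAP sentence, one model coefficient and one extra reported model. No new data are needed.

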3.2 Sensitivity analyses

Since we oversampled depressed women for the study, as a sensitivity/supplemental analysis, the linear mixed effects model analyses will be weighted using inverse probability sample weights, in which case maximum likelihood (ML) will be used, since REML is invalid in the presence of sampling weights.

Additionally, we will adjust the models for assessor (to examine the sensitivity of the model results to assessor).

3.3 Moderator analyses

Secondary analyses focus on potential moderators (effect modifiers) of any main associations with the primary outcomes. *A priori*, we hypothesize the following baseline variables may impact the degree to which the intervention affects depression symptoms, with their specific categorizations given in Table 2: socioeconomic status (education, asset index), maternal education (none vs. any) household composition (nuclear family status), child gender, the presence of intimate partner violence, treatment expectations (very/moderately useful vs. somewhat/not useful), maternal age (18-24 vs. 25+), depression severity (PHQ-9 = 10-14 vs. 15+), and depression chronicity (<12 weeks vs. ≥12 weeks). For the maternal outcomes, we will also look at parity (4+ kids vs. <4 kids) as a moderator. We will test for moderation of the effect by including these potential moderators in the model as an interaction between the potential moderator and the intervention indicator. Specifically, for our primary outcomes, we now have:

$$Y_{jk} = \alpha_1 + \beta_1 X_{jk} + \beta_2 M_{jk} + \beta_3 X_{jk} M_{jk} + \beta_4 U_k + \beta_5 C_{jk} + b_{0k} + \epsilon_{jk},$$

$$b_{0k} \sim N(0, \sigma_{b_{0k}}^2), \epsilon_{jk} \sim N(0, \sigma_{\epsilon_{jk}}^2)$$

where X_{jk} is the indicator of perinatally depressed intervention vs. control (1 if intervention; 0 if control) for mother i in cluster j and M_{jk} is the moderator variable for mother-child dyad j in cluster k . Other parameters are defined as in Section 3.1.1. β_3 tests the strength of the effect modification, and intervention effects by levels of the moderators can be estimated from this model.

4 References

3. Julious SA. Tutorial in biostatistics - Sample sizes for clinical trials with normal data. *Stat Med*. 2004;23(12):1921-1986.

BSITD-III	An individually administered assessment of the child’s achievement of developmental milestones across two areas: fine motor and receptive language. ²⁵	The total score from each domain, rescaled using the provided age-scaled score.	The standard scores are derived from the U.S. norms; and, because there are no available Pakistani norms, the scores provide a metric with which to compare groups of children in this Pakistan setting relative to the study hypotheses.
SCID	Structured clinical interview for depression. ²⁶	Prevalence of depression	
Other Outcomes			
Recurrence	Only measured in prenatally depressed. This measures in those who recovered by 6 months (based on SCID), how many had a recurrence of depression (based on SCID) by 36 months?		
SCID across time	Prevalence of depression from baseline through 36 months, all fit in one longitudinal model.		
Child Anthropometrics	Weight-for-age and height-for-age z-scores, based on WHO criteria		

Table 2. Moderators

Measure	Description
Socio-economic status (SES)	Asset-based SES index (dichotomized at the bottom 1/3 of the distribution) Maternal education (dichotomized at no education)
Household composition	Nuclear family status (nuclear vs. non-nuclear)
Intimate partner violence (IPV)	Any type of IPV in the past 12 months
Child Gender	
Treatment Expectations	Very/moderately useful vs. somewhat/not useful
Maternal age	18-24 vs. 25+
Depression severity	PHQ-9 = 10-14 vs. 15+
Depression chronicity	<12 weeks vs. ≥12 weeks
Parity*	<4 kids vs. 4+ kids

* Only considered a moderator for maternal outcomes

[figure not shown]

Figure 1.

[figure not shown]

Figure 2.

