Bachpan Trial Analysis Plan

Version 5.0

October 14, 2019

Contents

1	Purpose and scope.....	3
2	Description of the Trial	3
2.1	Principal research objectives and hypotheses to be addressed	3
2.1.1	Primary and secondary outcomes.....	4
2.2	Trial Design	4
2.3	Randomization	4
2.4	Sample size calculation.....	4
2.5	Intervention	5
2.6	Enhanced Usual Care (Control condition).....	6
2.7	Time of outcome assessment and visit windows	7
2.8	Data management	7
3	Data Analysis Plan.....	7
3.1	Analysis of primary and secondary outcomes	8
3.1.1	Analysis models and code.....	9
3.2	Sensitivity analyses	10
3.2.1	Moderator analyses.....	10
4	References.....	11
5	Tables and figures.....	13

1 Purpose and scope

This document provides the plan of analysis (statistical analysis plan) for the South Asian Hub for Advocacy, Research, and Education for mental health (SHARE) Child trial in Pakistan, conducted between October 2014 and August 2019. In Summer of 2018, the trial was renamed Bachpan. This plan covers the primary analysis comparing intervention arms and depressed and non-depressed perinatal women on their depressive symptoms at 36 months of age, in addition to comparing their children on various developmental outcomes at 36 months of age.

2 Description of the Trial

The Thinking Healthy Program (THP) is a community health worker (CHW)-delivered intervention which was developed in Pakistan and shown to have beneficial effects on both maternal depression and short-term child outcomes.

The current trial is described in detail in Turner et al.¹ In brief, the peer-delivered version of the THP was developed because of the lack of resources in many low and middle income (LMIC) countries to have professionals deliver the intervention. The present trial (THPP+) began in October 2014, and is an extension of the Thinking Healthy Program Peer-Delivered (THPP) trial, which is a six-month intervention delivered to women with perinatal depression, with the goal of reducing the burden of perinatal depression.² THPP+ is an extension of THPP in two ways: we follow the same sample of perinatally depressed women an additional 30 months; we recruited a sample of perinatally non-depressed women equal in sample size with the perinatally depressed group, and follow them for a total of 36 months, as well.

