2.3 Randomization

Within each of the 11 union councils of the sub-district, village clusters were randomized to Intervention or Usual Care control using a 1:1 allocation ratio. Randomization was done before the participants were recruited. Research teams responsible for identifying, obtaining consent and recruiting trial participants were blind to the allocation status (to minimize the post-randomization recruitment bias). Randomization was stratified by union councils, to help minimize the imbalance between arms by factors likely to be associated with the primary outcome and reduce the between-cluster variability, hence increasing the power of the study. Allocation of clusters was carried out by an independent statistician based at the London School of Hygiene and Tropical Medicine (LSHTM) using a computerized randomization sequence.

The trial PI, site PIs/coordinators, trial statisticians and members of the Trial Steering Committee were blinded to the allocation status until the analysis of the six-month data for the parent trial, SHARE.

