2.5 Intervention

The intervention for moderate-severe perinatal depression being assessed in these trials was the Thinking Healthy Program Peer-Delivered (THPP). THPP is the adapted version (peer-delivered) of the Thinking Healthy Program (THP) originally developed and evaluated (based on delivery by government-

employed LHWs) in Pakistan.⁹ THP has recently been adopted by the World Health Organization (WHO) for global implementation (http://www.who.int/mental_health/maternal-child/thinking_healthy/en/).

THPP comprises up to 14 sessions. The core strategies used by the peers are: active listening, collaboration with the family, guided discovery, homework, and behavioral (patient) activation (identifying and replacing unhealthy behaviors with healthy ones and practicing them).

The intervention begins in the third trimester of pregnancy, and includes ten home-based individual face-to-face sessions and four group-based sessions (given in the LHW women's group meetings) until the sixth month postnatally. Part of the task sharing by peers is to assist LHWs in organizing and conducting these mandatory routine women's groups and to encourage trial participants to attend these sessions. The following description comes from Atif et al. (2019).¹⁰

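### Recurrence is counted only among women who recovered by 6 months, a state the intervention aims to change, so any arm comparison on that denominator is not randomised

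*SAP*

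**What the plan says.** SAP Table 1, under Other Outcomes, describes Recurrence as "Only measured in prenatally depressed" and asks, "in those who recovered by 6 months (based on SCID), how many had a recurrence of depression" on SCID by 36 months. No model, estimand or descriptive label is attached to it. The next row, SCID across time, is "Prevalence of depression from baseline through 36 months, all fit in one longitudinal model" and carries no recovery restriction.

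Three other places bear on the definition:

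- SAP 2.3: "Randomization was done before the participants were recruited".
- SAP 2.5: "The intervention begins in the third trimester of pregnancy". The core sessions run to the sixth postnatal month, and booster groups then continue until the child is 3 years old.
- SAP 2 gives the aim of the six-month programme as lowering the burden of perinatal depression.

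On analysis, SAP 3 says that every analysis centres on comparing three groups: depressed intervention, depressed control and non-depressed. SAP 3.1 refers the reader to Table 1 for the outcomes and assigns binary outcomes a log-link Poisson GEE that yields prevalence ratios.

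**The concern.** The denominator is fixed after randomisation, by something the intervention is meant to change. If the programme works, the recovered set in the intervention arm contains women who would not have recovered under control. Their relapse risk may differ from that of women who would have recovered anyway. The arms can then differ on recurrence although treatment has no effect on relapse in anyone.

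The risk of misreading is practical. The booster phase covers the period in which recurrence is counted, so a reader would naturally take an arm difference in recurrence as the effect of the boosters. The difference could point either way, and it could contradict the result for all depressed women.

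**Working it through.** **Which comparison is possible.** Recurrence is measured only in depressed women, so the non-depressed group drops out. Of the three-group comparison in SAP 3, only intervention versus control remains.

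**Does anything correct for the selection?** The covariate rule in SAP 3.1 adds variables imbalanced at baseline or by loss to follow-up. It is written for primary analyses at a single time point, so it may not reach Recurrence at all. If it did, it would still not be aimed at imbalance created by keeping only recovered women. Intention-to-treat is stated for the primary analyses only.

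**Size, as an illustration.** The plan gives no recovery, relapse or power figure for Recurrence, so there is nothing to reproduce.

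Inputs:

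- Recovery RI = 0.65 (intervention) and RC = 0.45 (control). These are borrowed from SAP 2.4, where they are 36-month remission planning rates, so the time point differs, and the instrument too (Table 1 ties remission to the PHQ-9).
- k, the relapse rate of women who recover in one arm only, relative to women who recover in either arm. Assumed, 0.5 to 2.
- No true effect of treatment on relapse.

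If no woman recovers only under control (monotone recovery):

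ratio = [RC + (RI − RC) × k] / RI

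| k | Calculation | Ratio |
|---|---|---|
| 0.5 | (0.45 + 0.10)/0.65 | 0.85 |
| 1 | (0.45 + 0.20)/0.65 | 1.00 |
| 1.5 | (0.45 + 0.30)/0.65 | 1.15 |
| 2 | (0.45 + 0.40)/0.65 | 1.31 |

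The extra recoverers are 0.20/0.65 = 31% of the recovered intervention women.

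**Smaller recovery gap.** With 55% versus 45%, k = 0.5 gives 0.50/0.55 = 0.91 and k = 2 gives 0.65/0.55 = 1.18.

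**Relaxing monotone recovery.** Let a share d recover only under control, with the same k:

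ratio = {[(RC − d) + (RI − RC + d)k]/RI} / {[(RC − d) + dk]/RC}

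- d = 0.05: k = 0.5 gives (0.525/0.65)/(0.425/0.45) = 0.86; k = 2 gives (0.90/0.65)/(0.50/0.45) = 1.25.
- d = 0.10: k = 0.5 gives (0.50/0.65)/(0.40/0.45) = 0.87; k = 2 gives (0.95/0.65)/(0.55/0.45) = 1.20.

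**How the message can reverse.** Take monotone recovery at 65% versus 45%, k = 2, an assumed 20% relapse in the other recovered women, and no loss. Percentages of all depressed women:

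| | Intervention | Control |
|---|---|---|
| Not recovered | 35 | 55 |
| Recovered then recurred | 45 × 0.2 + 20 × 0.4 = 17 | 45 × 0.2 = 9 |
| Recovered and stayed well | 65 − 17 = 48 | 45 − 9 = 36 |

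Among recovered women, recurrence is 17/65 = 26.2% versus 9/45 = 20.0%, which looks unfavourable to the intervention. Among all depressed women, 48% versus 36% recovered and stayed well, which favours it.

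**The case against.** The strongest reply is that the SAP never orders a between-arm test here. Table 1 asks how many women recurred, which can be read as a count. The GEE and covariate rules sit under a heading for primary and secondary outcomes, and Recurrence is neither. The objectives in SAP 2.1 do not mention recurrence and SAP 2.4 gives no power for it. Lasting benefit is already covered by outcomes without the restriction. The illustration rests on assumed relapse rates and borrowed recovery rates.

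All of this stands, and it limits the point. A reader might infer that the SAP prespecifies a tested prevalence ratio for Recurrence; it does not. What remains is that SAP 3 is a general section whose comparison rule exempts no outcome, that only one contrast is left for this one, and that no wording calls it descriptive.

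It can also be said that a breakdown of all enrolled women depends on when loss occurs. That is true. In the k = 2 example with 20% loss unrelated to outcome, the not-recovered share is 28% versus 44% if all loss precedes 6 months. It is 35% versus 55% if all loss follows, with no earlier recurrence recorded; missing status is then 0.2 × 65 = 13% versus 0.2 × 45 = 9%. This is why missing status needs its own column. It is not a reason to keep only the selected denominator.

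**Conclusion.** The point holds in a limited form. Any intervention-versus-control comparison of Recurrence as defined is a non-randomised comparison. The plan makes such a comparison likely without ordering it, and nothing in the plan corrects for the selection.

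The size and direction of bias cannot be known from the documents. Under the stated assumptions, with no true effect on relapse, the ratio runs from 0.85 to 1.31 at 65% versus 45% recovery. The range is narrower with a smaller recovery gap or with some control-only recovery, and under this model there is no bias when the extra recoverers relapse at the same rate as the others. A reader might infer that the intervention will look worse than it is, or better; the documents support neither.

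Nor do they support extending the concern to the main results. Recurrence is an Other outcome, and no primary or secondary conclusion depends on it.

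**What to change.** State in the SAP that recurrence among recovered women is reported descriptively by arm, without a between-arm test and with a note that the groups are not randomised.

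Beside it, report by arm, with all enrolled depressed women as denominator, the percentages:

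1. not recovered by 6 months;
2. recovered and stayed well;
3. recovered then recurred;
4. SCID status missing.

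Draw between-arm inference on lasting benefit from the unrestricted outcomes already planned: 36-month PHQ-9, 36-month SCID and SCID across time.

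Two optional clarifications:

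- Name the SCID visits after 6 months that count. SAP 2.7 says only, "Outcome data (depending on the outcome) are collected at 3, 6, 12, 24, and 36 months postnatal". If 36 months is the sole later SCID visit, staying well means a single check.
- Label any added sustained-recovery contrast exploratory. The PIs and trial statisticians "were blinded to the allocation status until the analysis of the six-month data for the parent trial, SHARE", and SAP version 5.0 is dated October 2019 for a trial "conducted between October 2014 and August 2019".

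The cost is a few sentences and one descriptive table, with no new endpoint, test or data. The downside is that relapse among recovered women gets no formal test.
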